8.3 Secondary study parameter(s)

The courses over time and the difference between the groups will also be analyzed for the secondary outcomes. The continuous variables like quality of life of the caregiver, nutritional status (hand grip strength, PG-SGA), nutritional intake and performance scale will be analyzed the same way as the primary outcome. The course over time and the difference between the groups in medication use like anti-emetics e.g. will be treated as a dichotomous outcome (yes/no) and analyzed by using the Chi-square test. The difference in patient satisfaction and severity of symptoms between the two groups will be analyzed using the independent samples t-test.

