2. OBJECTIVES

Primary objective:

To study whether FoodforCare at Home is superior to usual care with respect to quality of life in advanced abdominal cancer patients undergoing chemotherapy.

Secondary objectives:

1. To reduce diet-related symptoms in these patients by using FoodforCare at Home compared to usual care.
2. To improve nutritional intake (adequate protein and energy intake) in these patients by using FoodforCare at Home compared to usual care.
3. To improve the nutritional status of these patients by using FoodforCare at Home compared to usual care.
4. To improve the functional status of these patients by using FoodforCare at Home compared to usual care.
5. To reduce medication use for the purpose of treating diet-related symptoms in these patients by using FoodforCare at Home compared to usual care.
6. To improve quality of life of the partners/caregivers of these patients by using FoodforCare at Home compared to usual care.
7. To improve patient satisfaction towards nutrition in these patients by using FoodforCare at Home compared to usual care.

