4.2 Inclusion criteria

In order to be eligible to participate in the study, the patient must meet all of the following criteria:

- age 18 years or older
- diagnosed with advanced colon or gynecological cancer
- receiving primary or secondary palliative chemotherapy according to a three weekly schedule
- living within a 40 km radius around the Radboud University Nijmegen Medical Centre
- written informed consent

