4.4 Sample size calculation

The sample size calculation is based on the primary outcome of this study: the EORTC-QoL-C30 questionnaire for quality of life. The primary outcome of this study is the difference in quality of life between the 2 groups at the start of the 3rd cycle of chemotherapy. Based on literature, advanced cancer patients with gynecological tumors and tumors of the colon have a mean score of approximately 60 points with a standard deviation of 22 points on the EORTC-QoL-C30 questionnaire. Assuming a difference of 10 points, on a scale of 0-100 points, is a clinically relevant difference in favor of FoodforCare at Home, we estimate that 76 patients are needed in each group in order to obtain a power of 80% (two-tailed t-test, alpha=0.05). Assuming a drop-out rate of 20%, this means a total of 180 patients. In order to improve the power significantly, we will make use of the ANCOVA test [31]. By multiplying the number of patients with $(1-(\rho^2))$ a total of 164 patients will be needed. The correlation between the baseline and follow-up outcome T2 (ρ) is estimated at 0.3.

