Medication use will be evaluated at every time point by obtaining information from the medical file of the patients. Information will be cross-checked by the researcher on doses and frequency of medication use. During the intervention period, medication use will be assessed by asking patients to log on a diary when they used which medication including dosage.

Symptoms:

To assess the number and the severity of symptoms experienced by the patients, they are asked to fill in the 'Utrecht Symptoom Dagboek' every day for 3 weeks during the intervention period. This is a diary based on the ESAS which consists of 12 symptoms which are frequently experienced by palliative cancer patients [46]. On a scale from 0 to 10, patients can score the severity of the symptoms with 0 indicating no symptom and 10 indicating the worst possible symptom.

Patient satisfaction:

The Net Promoter Score (NPS) with additional questions will be used to assess patient satisfaction in the intervention group at time point 3. The NPS is determined by asking the question: 'How likely is it that you would recommend FoodforCare to a friend or colleague?'. The score ranges from 1-10 and patients can be grouped in 'promoters' (9-10 grading), 'passively satisfied' (7-8 grading) and 'criticasters' (0-6 grading). The NPS is finally calculated by subtracting the percentage of criticasters from the percentage of promoters [47]. Additional questions about satisfaction with respect to the food supply and logistics of FoodforCare at Home will be answered by the patients to explain their score. The control group will also receive a questionnaire about their wellbeing and way of shopping and cooking. Both questionnaires are self-composed and based on validated questionnaires because there is no Dutch validated questionnaire available about a home-delivered meal service.

During the pilot study, participants in the intervention group are asked to participate in an in-depth interview instead of the questionnaire. This interview will be led by one of the researchers. It will generate information about the home-delivered meal service so it can be improved when implemented in the RCT.

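### The yes/no medication endpoint is not limited to symptom-driven use as objective 5 requires, so any regimen-linked anti-emetic use would dilute a true difference

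*Combined protocol and SAP*

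**What the plan says.** Section 2, secondary objective 5, reads: "To reduce medication use for the purpose of treating diet-related symptoms in these patients". The objective is therefore restricted by the purpose of the medication.

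Section 6.1.2 gives two data sources. The first is the file: "Medication use will be evaluated at every time point by obtaining information from the medical file of the patients". It adds: "Information will be cross-checked by the researcher on doses and frequency of medication use". The second is a patient record kept during the intervention period: "medication use will be assessed by asking patients to log on a diary when they used which medication including dosage". The diary items listed are time, drug and dose. The reason for use is not among them.

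Section 8.3 states the analysis: the course over time and the group difference "in medication use like anti-emetics e.g. will be treated as a dichotomous outcome (yes/no", with a Chi-square test. It does not say which of the two sources supplies the *yes*, over what window, for which medicines or for what purpose.

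On timing, section 4.2 admits patients "receiving primary or secondary palliative chemotherapy according to a three weekly schedule". Section 3 and Table 1 place the second and third measurements at the 2nd and 3rd cycles. The Summary names anti-emetics as the medication whose use the meals might reduce.

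**The concern.** The outcome analysed is broader than the objective it serves. Every participant is on chemotherapy, and two of the four file readings are taken at a cycle. If some patients have an anti-emetic on file because it belongs to their regimen, they score *yes* whether or not they took anything for symptoms. Someone with only the scheduled drug and someone who also needed extra doses for nausea then look the same.

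The stake is how a null result would be read. Pooling the two kinds of use does not create a false benefit. It pulls the arms together, so a report of no difference in anti-emetic use could reflect the endpoint rather than the meals. Randomisation is stratified on type of chemotherapy (section 6.3), which helps to balance regimen-linked use between arms but does not undo the dilution.

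**Working it through.** **The plan's own figures.** No rate, effect or power is stated for the medication endpoint. The sample size rests on quality of life alone: "76 patients are needed in each group in order to obtain a power of 80% (two-tailed t-test, alpha=0.05". With a 10-point difference and an SD of 22 (section 4.4), n = 2 × (1.960 + 0.842)² × 22² / 10² = 76 per group, which reproduces the plan's figure. The stated 180 × (1 - 0.3²) = 163.8, or 164. Less the plan's 20% drop-out, this leaves 164 × 0.8 / 2 = 65.6, taken as 66 per arm.

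**Dilution.** Let s be the proportion with symptom-driven use and r the proportion who score *yes* from regimen-linked use. Assume that r is the same in both arms and independent of s. Then

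P(yes) = r + (1 - r) × s,

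so the difference between arms is (1 - r) × (s_control - s_meals). This holds for any rates.

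**Power.** Normal approximation for two proportions, two-sided 0.05:

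power = Φ[(d - 1.96 × SE0) / SE1], with SE0 = √(2 p̄(1 - p̄)/n) and SE1 = √((p1(1 - p1) + p2(1 - p2))/n).

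Assumed symptom-driven use is 50% (control) versus 30% (meals), n = 66 per arm.

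- r = 0: SE0 = 0.0853, SE1 = 0.0835; (0.20 - 0.1672)/0.0835 = 0.39; power 65%.
- r = 0.5: SE0 = 0.0798, SE1 = 0.0793; (0.10 - 0.1564)/0.0793 = -0.71; power 24%.

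| r | Control vs meals, any use | Difference (points) | Power |
|---|---|---|---|
| 0 | 50% vs 30% | 20 | 65% |
| 0.25 | 62.5% vs 47.5% | 15 | 41% |
| 0.5 | 75% vs 65% | 10 | 24% |
| 0.7 | 85% vs 79% | 6 | 14% |
| 0.9 | 95% vs 93% | 2 | 7% |

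For 80% power the number needed per arm would be 93 at r = 0, 172 at r = 0.25, 329 at r = 0.5 and 2,213 at r = 0.9.

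**Other assumed rates** (65 per arm, rounding 65.6 down):

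- 60% versus 40%: power 63% at r = 0, 42% at 0.25, 26% at 0.5 and 11.5% at 0.8.
- 70% versus 45%: power 83% at r = 0, 63% at 0.25, 41% at 0.5 and 17% at 0.8.

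The pattern does not depend on the pair chosen. How much power is lost depends on r, which the documents do not give.

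**The case against.** The strongest reply is that the premise of frequent regimen-linked use is not in the documents. No section says that anti-emetics are given routinely with each cycle, and none gives a rate. That stands. A reader might infer that both arms sit near the ceiling, but this needs a high r that the documents do not supply. The point can only be made conditionally, with a range.

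A reader might also infer that the plan scores any anti-emetic as *yes*. It does not say so; the category is undefined. Section 8.3 could be read together with objective 5 so that the purpose limit carries over. That reading is possible, but 8.3 does not state it, and without a recorded reason for use it could not be applied reliably afterwards.

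Third, a reader might infer that objective 5 cannot be answered. That goes too far. The diary records time, drug and dose, and the file adds dose and frequency. Anti-emetics are only an example, so a problem in that class need not defeat the whole objective. Table 1 also has readings before chemotherapy and three months after T3. Most of the material for a better outcome is already collected.

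Finally, this is one of seven secondary objectives in a trial sized for quality of life, and even the separated outcome has only about 65% power under the 50% versus 30% assumption. That stands too: the change removes the dilution but does not make this a well-powered comparison.

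**Conclusion.** The concern holds in conditional form. The mismatch between objective 5 and the outcome in 8.3 is on the page and needs no outside knowledge. Its consequence depends on r. Under 50% versus 30% and 66 per arm, power drops from 65% to 41% if a quarter of patients have regimen-linked use, to 24% if half do, and to 7% if nine in ten do. A ceiling is therefore not needed for harm: at r = 0.25 more than a third of the power has gone (1 - 41/65 = 37%).

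The assumptions are the two symptom-driven rates, r itself, equal r in both arms, and independence of the two kinds of use. The documents support none of these numerically. As the outcome is specified, a null finding should not be taken as evidence that the meals leave symptom-driven medication unchanged. The primary analysis is not affected.

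**What to change.** In 6.1.2 and 8.3, define the medication outcome as symptom-driven use (as needed or newly added) of anti-emetics and other medication for diet-related symptoms, from T2 to T3. Take it from the medication diary already kept in that period, and add one item giving the reason for each use: scheduled, or for symptoms.

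Classify anti-emetics scheduled with the regimen from the medical file, without knowledge of arm. Count additions to them that were prompted by symptoms as symptom-driven, so that such changes are not lost. Report scheduled use by arm descriptively.

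The rule should be fixed before data are classified, because section 6.3 says the coordinating researcher cannot be blinded. The cost is one extra diary item for patients and a coding step for staff. No treatment or visit changes.

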3. STUDY DESIGN

A randomized controlled trial will be performed in palliative abdominal oncology patients at home. Inclusion will take place at the department of Medical Oncology at the start of palliative chemotherapy. The study is intended to be performed from March 2017 to July 2018. Patients will be randomly assigned to one of two groups before the start of the second cycle of chemotherapy because it is expected that FoodforCare at Home will make the largest difference during this cycle. The intervention group will receive meals from FoodforCare at Home and the control group will continue their regular diet for three weeks from the second cycle of chemotherapy until the next cycle of chemotherapy. Before the start of this study, a pilot study will be performed to determine whether the intervention is feasible in terms of logistics and delivery of the meals for example.

Measurements will take place at four time points during the study period i.e. before the start of chemotherapy, at the 2nd cycle of chemotherapy, at the 3rd cycle of chemotherapy and three month after T3 (figure 1). These measurements will be performed by AYA's/research assistants who will visit the patients at home. Time point 1, before the start of chemotherapy, will serve as the baseline measurement. At this moment, informed consent will be obtained and signed by the patient and the MUST score will be determined. Quality of life of patient and caregiver, nutritional intake, nutritional status, functional status and medication use will be assessed at all time points. For quality of life, the EORTC-QoL-C30 questionnaire will be filled in by the patients and the Caregiver Reaction Assessment by their caregivers. Nutritional status will be assessed using the handgrip strength measurement, the PG-SGA and performance scale by means of the Karnofsky score and the SPPB. Data on nutritional intake will be recorded using a 3-day food diary, which the patients will fill in by themselves. Medication use will be obtained from the patient's medical file. Additionally, during the intervention period, patients will record their symptoms using 'Utrecht Symptoom Dagboek' and medication use will be assessed by using a diary. At time point 3, patient satisfaction in the intervention group will be assessed by the Net Promoter Score with additional questions. An overview of the measurements can be found in table 1.

Figure 1. Flowchart of the study design of the FoodforCare at Home study.

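### The chi-square test planned for medication use cannot test its course over time, and the timing and dosage logged in the diary have no planned inferential use

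*Combined protocol and SAP*

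**What the plan says.** Secondary objective 5 (section 2) reads: "To reduce medication use for the purpose of treating diet-related symptoms in these patients by using FoodforCare at Home compared to usual care". It does not say whether a reduction means fewer users, fewer days or lower doses.

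Section 3 states: "Measurements will take place at four time points during the study period". These are before chemotherapy (T1), at the second cycle (T2), at the third cycle (T3) and three months after T3. The meals run from the second cycle to the next. Table 1 lists medication use at all four points.

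Section 6.1.2 describes two sources. The first is the medical file: "Medication use will be evaluated at every time point by obtaining information from the medical file of the patients", and "Information will be cross-checked by the researcher on doses and frequency of medication use". The second is a diary kept during the three-week intervention period, in which patients are asked to "log on a diary when they used which medication including dosage".

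Section 8.3 gives the only analysis: "The course over time and the difference between the groups in medication use", with anti-emetics as the example, "will be treated as a dichotomous outcome (yes/no) and analyzed by using the Chi-square test". Continuous secondary outcomes, by contrast, follow the primary outcome, for which section 8.2 plans repeated-measures mixed models.

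**The concern.** One test is assigned to two questions, and it can answer at most one of them. A Pearson chi-square compares proportions between independent groups. It does not link a patient's measurements, has no visit effect or group-by-visit interaction, and does not adjust for use before the meals. The plan applies a repeated-measures method to its continuous repeated outcomes but none to this binary one.

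Section 8.3 also does not say which visit or window defines a yes, or which drugs count. Without that, several comparisons are possible and none is named in advance.

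Finally, the yes/no coding makes no use of the frequency and dosage that patients and staff are asked to record. Reduced medication use, especially of anti-emetics, is a benefit put forward in the summary and a formal objective. As planned, the trial could fail to detect a real reduction in how often patients need these drugs.

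**Working it through.** The documents give no rate, effect size or power for medication use, so there is no stated figure to reproduce. The check asks what the chi-square test delivers under each way of running it.

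**Inputs from the documents.** Four time points (section 3, Table 1); 164 patients in two groups (section 5.1), which is 82 per arm if allocation is 1:1 (the ratio is not stated); 20% drop-out (section 4.4), so 82 × 0.8 = 65.6, about 66 per arm; a three-week diary, 21 days (sections 5.1 and 6.1.2).

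**1. Separately at each visit.** Each test is a valid comparison of the arms at that visit. T1 and T2 come before the meals, so they cannot show an effect. T3 and the 3-month visit can, but two separate tests do not test change over time or a group-by-time difference, and neither adjusts for earlier use.

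**2. Between visits within an arm.** This treats paired observations from the same patients as independent. It also does not compare the arms.

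**3. Pooled over visits.** Each patient counts up to four times. With four visits and a common within-patient correlation ρ, the design effect is DE = 1 + 3ρ. The actual type I error at nominal two-sided 5% is 2 × (1 − Φ(1.96/√DE)). The values of ρ are assumptions.

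| ρ | DE | Type I error, formula | Type I error, simulation |
|---|---|---|---|
| 0.3 | 1.9 | 15.5% | 15.5% |
| 0.5 | 2.5 | 21.5% | 22.0% |
| 0.7 | 3.1 | 26.6% | 27.2% |

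The simulation used beta-binomial data, 82 per arm, 60% use (assumed) and 20,000 replicates.

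**4. Yes/no against days of use.** This illustration rests on assumed rates throughout. The share of patients with any use over 21 days is 80% or 90% in both arms. Control users take medication on a mean of 30%, 40% or 50% of days, varying between patients (beta distribution with parameters summing to 3, at least one day per user). In the meal arm that mean is 30% lower in relative terms. There were 2,000 replicates per setting.

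| Patients per arm | Power, chi-square on any use | Power, rank test on days |
|---|---|---|
| 66 | 4-6% | 32-73% |
| 82 | 4-6% | 36-81% |

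The chi-square result follows from the set-up. The share of users is the same in both arms, so the test rejects at about its nominal 5% whatever happens to the days. What the table adds is that the day count has useful, though not always high, power with this number of patients.

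**The case against.** The natural reading of a yes/no outcome with a chi-square test is one comparison per time point, and each such test is valid. That stands: a chi-square test at one prespecified visit after the meals would be an acceptable, if unadjusted, test of the group difference. It does not rescue the course over time, which section 8.3 assigns to the same test, and no visit is prespecified.

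A reader might infer that the planned analysis has a type I error of 16-27%. The documents do not support this. Those figures need the visits pooled as independent rows, which section 8.3 does not say, and the correlations are assumed.

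A reader might also infer that objective 5 is about days and doses and that the plan throws these data away. Objective 5 names neither, and a lower share of users is a legitimate reading of it. Descriptive reporting of days and doses is not ruled out by section 8.1. What can be said is that no inferential use of them is planned. Likewise, whether a patient who moves from daily to occasional use counts as unchanged depends on the window for a yes, and the documents do not define one.

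Lastly, the trial was sized on quality of life, and the documents claim no power for medication use. Limited power on this outcome is therefore not in itself a fault of the plan.

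**Conclusion.** The point holds as a mismatch between a stated question and a stated method. The chi-square test cannot analyse the course over time from four measurements per patient, and no other section supplies a method that can. This part needs no numerical assumption.

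Two further gaps stand on the text alone: the visit, window and drug classes that define a yes are not given, and the diary's timing and dosage have no planned inferential use. How much is lost by ignoring the diary is illustrative. With a 30% relative fall in days of use and the share of users unchanged, power is about 5% for yes/no against 32-73% for days with 66 per arm, all under assumed rates. The inflated type I error is conditional on pooling and should be read only as a reason to exclude pooling explicitly.

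This is one of several secondary outcomes. The sample size and the primary conclusion are unaffected. The change should be made, but the trial's main result does not depend on it.

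**What to change.** Amend section 8.3 as follows.

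- **Definitions.** State which medications count (for example, anti-emetics) and the window that defines a yes at each visit.
- **Yes/no use.** Analyse use at T3 and at 3 months with a GEE or mixed logistic model containing group, visit, group-by-visit and use recorded before the meals start. T1 and T2 enter as covariate only, not also as outcomes. Name the odds ratio at T3 as the contrast of interest. Include the stratification factors (tumour type and type of chemotherapy, section 6.3) where the number of events allows.
- **Diary.** Add a between-arm comparison of the number of days with anti-emetic use over the three weeks, by a rank-based or count model, adjusted for file-recorded use before the meals. Note that this baseline comes from a different source, because the diary covers only the intervention period. Confirm that both arms keep the diary; section 6.1.2 refers to patients without limiting it to one arm.

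The cost is analysis wording and a little more analysis work, with no new data. The main drawback is that the logistic model may be sparse if nearly all patients are users, particularly since the number of chemotherapy strata is not given. In that case the stratification terms would have to be reduced, and the day count would be the more informative result.

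### Section 8.3 plans a between-arm t-test of patient satisfaction, but the protocol describes no satisfaction score that both arms complete

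*Combined protocol and SAP*

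**What the plan says.** Objective 7 in section 2 is a comparison with usual care: "To improve patient satisfaction towards nutrition in these patients by using FoodforCare at Home compared to usual care". Section 8.3 supplies the test: "The difference in patient satisfaction and severity of symptoms between the two groups will be analyzed using the independent samples t-test".

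The measurement is described in two places, and both restrict it to one arm. Section 3 says: "At time point 3, patient satisfaction in the intervention group will be assessed by the Net Promoter Score with additional questions". Section 6.1.2 repeats this and gives the content:

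- The NPS item asks: "How likely is it that you would recommend FoodforCare to a friend or colleague".
- The NPS is then aggregated: "The NPS is finally calculated by subtracting the percentage of criticasters from the percentage of promoters".
- The further questions are also about the product: "Additional questions about satisfaction with respect to the food supply and logistics of FoodforCare at Home will be answered by the patients".
- For the other arm: "The control group will also receive a questionnaire about their wellbeing and way of shopping and cooking".
- On the origin of the two forms: "Both questionnaires are self-composed and based on validated questionnaires".

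Table 1 marks patient satisfaction at the third cycle only. It does not separate the arms and names no instrument.

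**The concern.** An independent samples t-test compares the mean of one variable in two groups. Here the intervention arm rates a product that controls do not receive in the study, and controls answer a form on other topics. If the forms are used as described, there is no between-arm difference in satisfaction to estimate, and objective 7 has no answer.

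Two things follow. Items not asked at the third cycle (T3) cannot be recovered at analysis. And because section 8.3 names no score, someone could later set two unlike questionnaires against each other and report the result as a satisfaction difference.

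**Working it through.** The protocol gives no figure to reproduce on this point. The main check sets the planned test against what is measured.

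**Step 1: what the test needs.** With intervention (I) and control (C) arms, t = (mean_I − mean_C) / [s_p × √(1/n_I + 1/n_C)]. Each patient must contribute one value, and that value must mean the same thing in both arms.

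**Step 2: what is described (section 6.1.2).**

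| Component | Arm | Time | Subject | Usable in both arms? |
|---|---|---|---|---|
| NPS item | Intervention | T3 | Recommending FoodforCare | No |
| Additional questions | Intervention | With the NPS, to explain the score | Food supply and logistics of FoodforCare at Home | No |
| Control form | Control | Not stated in the text | Wellbeing, shopping, cooking | No shared item described |

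Two satisfaction components are described, and neither is given to controls. mean_C is therefore undefined.

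**Step 3: the NPS as a test variable.** The NPS is a difference of two percentages, so it gives one number per group and no patient-level spread. The individual ratings behind it could enter a t-test, but they exist in one arm only. Section 8.3 does not say which form is meant.

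**Step 4: other places that might resolve it.** The Summary lists satisfaction as a secondary endpoint and the Introduction expects a benefit on it; neither names an instrument. Table 1 gives a visit but no instrument, so it does not override the two sections that specify the intervention group.

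**Step 5: time left to fix it.** Section 4.2 requires a three-weekly chemotherapy schedule, so T3 at the third cycle falls 2 × 3 = 6 weeks after the first cycle. Section 5.1 gives 164 patients in 1.5 years, and section 4.4 a 20% drop-out. Assuming even accrual and equal arms:

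- 164 / 18 = 9.1 patients per month, or 4.6 per arm.
- After drop-out: 9.1 × 0.8 = 7.3 per month, or 3.6 per arm.

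The 18 months is not the only reading. Section 3 runs the whole study from March 2017 to July 2018, which is 17 months counted inclusively. If that includes follow-up to three months after T3 (about 1.4 + 3 = 4.4 months from the first cycle), accrual has about 17 − 4.4 = 12.6 months. The rate is then 164 / 12.6 = 13.0 per month (6.5 per arm), or 13.0 × 0.8 = 10.4 (5.2 per arm) after drop-out.

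**The case against.** The strongest reply is that the two questionnaires are not in the document. The control form is described under the patient satisfaction heading, as something controls also receive, and both forms are said to draw on validated instruments. Table 1 schedules satisfaction at the third cycle without restricting it to an arm. The control form may therefore have been meant as the counterpart and may hold a matching item.

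That stands as a possibility, and it limits the conclusion to the plan as described. It does not rescue the plan. The topics listed for the control form do not include satisfaction, the forms are self-composed so their content cannot be inferred from a known instrument, and section 8.3 names no score.

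Three smaller replies have some force. The NPS aggregation is not the main obstacle, since individual ratings exist; the missing control counterpart is. The monthly losses describe the cost of delay, not the size of the defect, and they depend on the accrual window. And this is one secondary objective, which is why the point calls for a correction and does not threaten the trial.

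**Conclusion.** The concern holds. As described, the satisfaction comparison in section 8.3 cannot be carried out, because no score common to both arms is described or named. The defect is one of kind: neither of the two described satisfaction components reaches the control arm. It affects one of seven secondary objectives. The primary outcome, sample size and safety are untouched.

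The conclusion assumes that the control form contains only what section 6.1.2 says. If it contains a matching satisfaction item, naming that item in section 8.3 closes the point. If not, each month of delay beyond the first T3 visit loses the common items for about 9 patients (about 7 after drop-out) over 18 months of accrual, or about 13 (about 10) over the shorter window. Patients who reach T3 after the items are added are not lost.

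The symptom half of the same sentence does not share this defect, because the 0–10 diary is described without restriction by arm. Section 8.3 still does not say how 12 symptoms scored daily for three weeks become one value per patient; that is a separate question.

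A minor related point in section 8.3: a chi-square test suits medication use at one named time point, but not its course over time, because it ignores repeated observations on the same patient.

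**What to change.** Before the first T3 visit:

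1. Put the same few items on both arms' forms, asking about satisfaction with one's own meals and nutrition over the past three weeks. State their scale and scoring.
2. State in section 6.1.2 that both forms are completed at T3.
3. Name that patient-level score in section 8.3 as the variable compared by t-test.
4. Report the NPS and the FoodforCare-specific questions descriptively in the intervention arm. Reconcile the NPS range as well: section 6.1.2 gives 1–10 but puts the lowest category at 0–6.

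If the control form already has a suitable item that is also asked in the intervention arm, steps 2 to 4 are enough. If no common item is added, restate objective 7 and section 8.3 as descriptive for the intervention arm.

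For medication use, name the time point for the chi-square test. If the course over time is wanted, use a logistic mixed model or GEE with group, visit and group-by-visit.

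The cost is a few items on two forms already planned and about two sentences in section 8.3, or only a rewording. The downsides are a slightly longer form, new items that are not validated (the planned forms are self-composed too, though drawn from validated ones), and ratings open to bias because patients know their arm.
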